6.3 Study Safety Monitoring Plan

All subjects will be assessed regularly for potential occurrence of adverse events (AEs) from the time of signing the informed consent form (ICF) until 16 weeks after the last dose. If consistent mild and/or moderate infusion reactions are observed, the Sponsor may recommend pretreatment of subjects. In the event that any subject experiences an acute infusion reaction considered to be a serious adverse event (SAE), a slower infusion rate for administration of the investigational product and/or a mandatory pre-medication regimen (e.g., anti-emetics, H1 or H2 blockers, and/or corticosteroids) may be introduced. Each investigative site must have trained staff and immediate access to emergency supplies and equipment including, but not limited to, drugs needed to treat a subject in case of a life-threatening emergency.

The Sponsor has primary responsibility for the ongoing medical review of safety data throughout the study.

Recommendations will be made with the input of the Medical Monitor to the Principal Investigator and other appropriate designated staff regarding further conduct of the study. Medical Monitoring meetings will be held on a regular basis to monitor the safety of the subjects and adherence to the protocol (e.g., inclusion and exclusion criteria, concomitant medications, and visits) in addition to the Safety Monitoring Committee meetings described below.

The Safety Monitoring Committee, which recommends dose-escalation and continuation of the study will meet prior to starting each cohort (based upon projected enrollment rate is anticipated to be approximately every 3 months) and as needed during the study. A separate Safety Monitoring Committee Charter will identify the membership and define the specific procedures of the committee.

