8.5 Prior and Concurrent Therapy

All medications (including prescription, non-prescription and supplements) for treatment of UC taken within 6 months prior to Screening; any other medication taken 1 month prior to Screening; and any concomitant medications (including tracking probiotic usage) during the study will be collected. For all biologic treatments, the reason for discontinuation should be collected at Screening. Combination medications should be recorded by trade name.

Stable doses of the following concomitant medications are permitted for UC treatment during the study as specified below:

- Aminosalicylates (5-ASA or mesalamine ≤ 4.8 g/day; sulfasalazine ≤ 3 g/day) for at least 14 days prior to the Screening visit; and/or
- Oral glucocorticoids, ≤ 20 mg/day prednisolone or the equivalent, or budesonide ≤ 9 mg/d for at least 14 days prior to the Screening visit (or for 4 weeks if a course of corticosteroids had started at less than 8 weeks prior to Screening visit); and/or
- Azathioprine up to 3 mg/kg/day or 6-mercaptopurine up to 1.5 mg/kg/day for a total treatment period of at least 12 weeks, including 4 weeks of stable treatment, prior to the Screening visit.

Supportive therapy to manage symptoms or AEs is acceptable. Daily, chronic antidiarrheals should not be taken.

One bolus or “rescue” treatment for up to 7 days with each of the following: systemic corticosteroids or topical corticosteroid enemas or suppositories (in addition to the dose of oral corticosteroids at Screening) is permitted only after Week 12 evaluations are complete. Topical anti-inflammatory agents may be permitted only after Week 12 evaluations are complete and application must be withheld for at least 2 weeks prior to the sigmoidoscopy at Week 52/End-of-Treatment visit.

Dose reductions of concurrent medications are permitted for AEs from Baseline through the end of the study as allowed by the protocol. Other dose adjustments of concurrent medications (including corticosteroids and other treatments for UC) are permitted after the Week 12 visit (per Investigator’s judgment), i.e., during OLE/LTE Therapy and the Induction Therapy and OLE/LTE Therapy Follow-up Periods. After the Week 12 visit, corticosteroid (glucocorticoid) dosages of prednisolone or its equivalent may be tapered by approximately 2.5 mg/day per week, at the Investigator’s discretion. Subjects who have recurrence of clinical symptoms may increase their chronic (> 7 days) dose of corticosteroids and other

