 - Glucocorticoid-free clinical remission at Week 52 will be defined in the case that clinical remission is present at Week 52 and no glucocorticoid listed in Section 9.3 is used from Week 16 through Week 52.
- Glucocorticoid dosages:
 - Baseline glucocorticoid dosages (times) will be defined as the total number of administrations of glucocorticoid listed in Section 9.3 that is used during Double-Blind Induction Period (from Day 1 to a day before Week 16). For the subject who receives no glucocorticoid, the dosages will be 0.

	Forms			
	Title	Statistical Analysis Plan Template		
	Code	Version	Effective Date	Page
	FRM_ST03_032	01	23 Apr 2015	32 of 53

- Glucocorticoid dosages (times) at Week 16 through Week 52 will be defined as the total number of administrations of glucocorticoid listed in Section 9.3 that is used during OLE/LTE Therapy Period (from Week 16 to Week 52). For the subject who receive no glucocorticoid, the dosages will be 0.
- Glucocorticoid dosages (times) at Week 16 through LTE Therapy Follow-up Period will be defined as the total number of administrations of glucocorticoid listed in Section 9.3 that is used during LTE Therapy Period and LTE Therapy Follow-up Period (from Week 16 to Follow-up 3). For the subject who receives no glucocorticoid, the dosages will be 0.
- Glucocorticoid dosages (times) at Week 16 through OLE Therapy Follow-up Period will be defined as the total number of administrations of glucocorticoid listed in Section 9.3 that is used during OLE Therapy Period and OLE Therapy Follow-up Period (from Week 16 to Follow-up 3). For the subject who receives no glucocorticoid, the dosages will be 0.
- If there is glucocorticoid that the number of administrations is unknown, it will be assumed that the glucocorticoid was used at a frequency of an administration per day.
- For the subjects who do not move to OLE/LTE Therapy Period, “Glucocorticoid dosages (times) at Week 16 through Week 52” and “Glucocorticoid dosages (times) at Week 16 through OLE/LTE Therapy Follow-up Period” will not be defined.
- Change from baseline in corticosteroid (glucocorticoid) dosages will be defined as follows:
 - Change from baseline in corticosteroid (glucocorticoid) dosages at Week 16 through Week 52 = Glucocorticoid dosages at Week 16 through Week 52 - Baseline glucocorticoid dosages

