 - Change from baseline in corticosteroid (glucocorticoid) dosages at Week 16 through LTE Therapy Follow-up Period = Glucocorticoid dosages at Week 16 through LTE Therapy Follow-up Period - Baseline glucocorticoid dosages
 - Change from baseline in corticosteroid (glucocorticoid) dosages at Week 16 through OLE Therapy Follow-up Period = Glucocorticoid dosages at Week 16 through OLE Therapy Follow-up Period - Baseline glucocorticoid dosages
- Duration of glucocorticoid-free treatment will be defined as the duration that no glucocorticoid listed in Section 9.3 is used from Week 16 through Follow-up 3.
 - Duration of glucocorticoid-free treatment (days) = Date of first glucocorticoid after Week 16 visit - Date of Week 16 visit
 - If the subject received glucocorticoid on the date of Week 16 visit, the duration of glucocorticoid-free treatment for the subject is 0.

A comparison between treatments (each KHK4083 dose level versus placebo) will be performed using an ANCOVA model with changes from Baseline in UCEIS, total Mayo Clinic score and partial Mayo Clinic score at Week 52 during Double-Blind Therapy Period as dependent variables, treatment as fixed effect and baseline value as covariate. The number of subjects and the number of subjects considered in the model will be provided by treatment. The adjusted means for treatments (least squares means) and the relative 95% CIs will be presented. The difference between the adjusted means for each treatment groups from placebo (Difference in Least Squares Mean from Placebo) will be calculated with the relative 95% CI and p-value. If ANCOVA cannot be applied

	Forms			
	Title	Statistical Analysis Plan Template		
	Code	Version	Effective Date	Page
	FRM_ST03_032	01	23 Apr 2015	33 of 53

due to the issue that the parameters cannot be estimated appropriately, these analyses using ANCOVA for Week 52 will not be applied.

Means with SDs for the efficacy variables (mMES, UCEIS, total Mayo score and partial Mayo score) at all visits will be performed graphically by each treatment (e.g. Placebo, 1.0 mg/kg, 3.0 mg/kg, or 10 mg/kg) and by Double-Blind Therapy Period and OLE Therapy Period. For partial Mayo score, Means with SDs as all visits will be performed graphically by “Double-Blind Therapy Period and Double-Blind Therapy Follow-up Period” and “OLE Therapy Period and OLE Therapy Follow-up Period”. Mean changes from Baseline will also be performed in the same manner.

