The derived variables will be identified in the listings with a flag (*).

Tabular display of data for prior / concomitant medications, and all tabular displays of adverse event data should be presented by the body system, drug class, or SOC with the highest occurrence in the active treatment group (KHK4083 combined group) in decreasing order. Within the body system, drug class and SOC, medical history (by Preferred Term), drugs (by ATC1 code), and adverse events (by Preferred Term) should be displayed in decreasing order. If incidence for more than 1 term is identical, they should then be sorted alphabetically.

In general, dates will be presented on listings in the format ddmmyyyy (date9.) and time in the format hh:mm (time5.). In case of partial dates or times, missing information will be replaced by dashes. Numeric variables will be listed generally with the same number of decimal places as in the actual data.

The following rules on decimal places will be considered in the listings for the derived variables (in the analyses approximations will not be performed):

- Age (years), duration of treatment (days): 0 decimal place;
- Change from baseline: same as the variable considered.

The following rules on decimal places will be considered for the results of the analyses (if the analyses are performed on derived variables, the level of precision of the actual data is derived from the previous list):

- Min, max: same as actual data;
- Mean and its confidence limits (unadjusted and adjusted), adjusted difference between means and its confidence limits, SD, median: actual data + 1 decimal;
- Percentage: 1 decimal place.

	Forms			
	Title	Statistical Analysis Plan Template		
	Code	Version	Effective Date	Page
	FRM_ST03_032	01	23 Apr 2015	39 of 53

9.3 **Glucocorticoid**

Among concomitant medications which started to be administered from Day 1, those corresponding to the list below will be defined as glucocorticoid and considered in Tables and Listings relative to glucocorticoid.

- Medications that ATC code is “H02AB” (that is assigned to “Glucocorticoids”).

	Forms			
	Title	Statistical Analysis Plan Template		
	Code	Version	Effective Date	Page
	FRM_ST03_032	01	23 Apr 2015	40 of 53

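### SAP 9.3 selects glucocorticoids by one ATC code and a start date, with no route or indication rule, so rectal and budesonide use may be missed and infusion pre-medication would count

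*SAP*

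**What the plan says.** SAP 9.3 sets two conditions. The first is timing: "Among concomitant medications which started to be administered from Day 1, those corresponding to the list below will be defined as glucocorticoid". The second is the code: "Medications that ATC code is “H02AB” (that is assigned to “Glucocorticoids"). Neither SAP 9.3 nor SAP 7.3 adds a route, formulation or indication.

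SAP 7.3 builds three outputs on this definition:

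- Glucocorticoid-free remission requires clinical remission at Week 52 and that "no glucocorticoid listed in Section 9.3 is used from Week 16 through Week 52".
- Glucocorticoid dosages are counts of administrations of the same drugs.
- Glucocorticoid-free duration is "the duration that no glucocorticoid listed in Section 9.3 is used from Week 16 through Follow-up 3", and is 0 if a dose falls on the Week 16 visit date.

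Protocol 8.5 permits as stable background treatment "Oral glucocorticoids, ≤ 20 mg/day prednisolone or the equivalent, or budesonide ≤ 9 mg/d". It also limits rescue to one course per steroid type, lasting no more than 7 days, and fixes its timing: "systemic corticosteroids or topical corticosteroid enemas or suppositories (in addition to the dose of oral corticosteroids at Screening) is permitted only after Week 12". On infusion reactions, Protocol 8.1.3.3 plans no routine pre-medication, but Protocol 6.3 says that after a serious acute reaction "a mandatory pre-medication regimen (e.g., anti-emetics, H1 or H2 blockers, and/or corticosteroids) may be introduced".

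**The concern.** The protocol treats budesonide and rectal corticosteroids as steroid treatment for ulcerative colitis. The SAP turns the steroid-sparing question into membership of one code, and neither document shows that the code covers those products. A subject who needed a steroid enema to stay well could be reported as having done without steroids.

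The rule can also err the other way. A systemic steroid given only to prevent an infusion reaction says nothing about control of the colitis, yet nothing exempts it. In both cases the derived result could describe something other than steroid sparing, and a reader of the tables would not see why.

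**Working it through.** The plan gives no figure to reproduce here. The check runs each steroid use that the protocol contemplates through the two conditions of SAP 9.3.

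| Steroid use | Protocol source | Starts from Day 1? | Coded H02AB? | Counted under SAP 9.3? |
|---|---|---|---|---|
| Oral prednisolone or budesonide, stable since before Screening | 8.5 | No | Immaterial | No, because of the start rule |
| Budesonide record that starts after Day 1 | 8.5 (dose adjustments allowed after Week 12) | Yes | Not shown in the documents | Depends on coding |
| Rectal corticosteroid rescue | 8.5, 8.1.4.2 | Yes, after Week 12 | Not shown in the documents | Depends on coding |
| Corticosteroid infusion pre-medication, if introduced | 6.3, 8.1.3.3 | Yes | If so coded | Yes, with no exemption |

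**Row 1** belongs to a different problem. Background use must be "Oral glucocorticoids, ≤ 20 mg/day prednisolone or the equivalent, or budesonide ≤ 9 mg/d for at least 14 days prior" to Screening, so on a literal reading the start rule removes it whatever its code. Oral prednisolone is removed in the same way.

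**Rows 2 and 3** pass the start rule, so the code alone decides. SAP 4.1 names the coding dictionary but not how one ATC code is chosen per record. Both outcomes are unsatisfactory:

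- If rectal steroids and budesonide fall outside H02AB, their use from Week 16 is invisible to all three outputs.
- If H02AB is assigned whatever the route, skin, eye and inhaled steroids for other conditions also count as steroid use.

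Whether row 2 occurs depends on how the eCRF records dose changes, which the documents do not say.

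**Row 4.** One qualifying record between Week 16 and Week 52 is enough to fail glucocorticoid-free remission.

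- Infusions from Week 16 to Week 48, every 4 weeks: (48 − 16)/4 + 1 = 9. Pre-medication at every one of them, an upper bound with one administration each, would add 9 to the dosage count.
- Possible glucocorticoid-free duration from Week 16 to Follow-up 3 at Week 64: (64 − 16) × 7 = 336 days. A dose on the Week 16 visit date makes it 0.

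**Effect of one misclassified subject on a rate**, at the planned randomised group sizes in Protocol 12.3.4:

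- One Part A dose group: 1/9 = 11.1 percentage points.
- Combined placebo: 1/15 = 6.7 percentage points.
- Recommended dose, Parts A and B: 1/27 = 3.7 percentage points.

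Groups in the extension may be smaller, and SAP 7.3 reports glucocorticoid-free remission separately for the double-blind and open-label periods. The shift per subject could therefore be larger.

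**The case against.** The strongest reply is that this is a gap in wording, not a demonstrated error. No document gives the ATC code of budesonide, enemas or suppositories. A reader might infer that permitted budesonide users are shown to count as steroid-free because of the code. The documents do not support that: the coding is unknown, and background budesonide is lost first to the start-date rule. A reader might also picture long-term rectal use going uncounted, but the rescue provision in Protocol 8.5 is limited to 7 days for each type. These limits stand. Even so, one short course is enough to matter, because SAP 7.3 requires no use at all.

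On pre-medication, a reader might infer a bias against active drug. The documents do not support this either. Pre-medication is not routine, corticosteroids are only one option, and under Protocol 8.1.3.3 a mandatory regimen would apply to all subjects. Only the optional pretreatment for milder reactions could differ by arm, and nothing indicates that it would. The objective also speaks of being glucocorticoid-free without tying this to colitis, so counting every glucocorticoid is a defensible literal reading. That argues for showing both versions, not for simply excluding pre-medication.

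Finally, the endpoints are exploratory, Protocol 12.3.5 applies no Type I error control, and none of these outputs is among the Week 12 tables in SAP 9.4.1. Concomitant medications are also tabulated and listed by subject, so the drugs remain visible. This lowers the severity, but it does not correct the derived results.

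**Conclusion.** The point holds as a minor one. SAP 9.3 states an operative selection rule that is not matched to the steroids the protocol names. The classification of rectal rescue, and of any budesonide record that starts after Day 1, rests on a code whose coverage the documents do not show. Any H02AB pre-medication from Week 16 through Week 52 would end glucocorticoid-free status without regard to its purpose.

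The first effect assumes that these products are coded outside H02AB. The second assumes that steroid pre-medication is introduced. The documents give no usage frequency for either, so the number of subjects affected cannot be estimated; only the effect per subject can. The loss of background steroid users through the start-date condition is a separate matter, and correcting the code alone would not repair it.

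**What to change.** In SAP 9.3, replace the single-code rule with a list of qualifying drugs and routes. Finalise it before database lock, without reference to treatment assignment where that is still blinded; the open-label extension and the unblinding after Part B limit how far this is possible.

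- Include systemic corticosteroids, oral budesonide and rectal corticosteroids.
- Leave out skin, eye and inhaled forms.
- Flag steroids given as infusion pre-medication or to treat an infusion reaction, and present the glucocorticoid-free results with and without them.
- Show rescue courses of up to 7 days in a separate row.
- Use the recorded indication only if the eCRF collects it, which the documents do not show.

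The cost is a paragraph in the SAP and a small medication review; the medications are already collected and coded. The glucocorticoid-free rate may come out slightly lower.

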9.4 Tables

Number	Title
Table 14.1-1	Disposition of Subjects / Summary of All Subjects
Table 14.1-2.1	Demographic Characteristics / Safety Analysis Set
Table 14.1-2.2	Baseline Assessment of Ulcerative Colitis / Safety Analysis Set
Table 14.1-2.3	Demographic Characteristics / Full Analysis Set
Table 14.1-2.4	Baseline Assessment of Ulcerative Colitis / Full Analysis Set
Table 14.1-3.1	Prior Medications / Safety Analysis Set
Table 14.1-3.2	Concomitant Medications During Induction Period / Safety Analysis Set
Table 14.1-3.3	Concomitant Medications During Double-Blind Long Term Extension and Follow-Up Therapy / Safety Analysis Set
Table 14.1-3.4	Concomitant Medications During Open-Label Extension Therapy Period and Follow-Up Therapy / Safety Analysis Set
Table 14.1-4.1	Medical and Surgical History / Safety Analysis Set
Table 14.1-4.2	Concomitant Diseases / Safety Analysis Set
Table 14.1-5	Exposure to Investigational Product During Induction Therapy Period / Safety Analysis Set
Table 14.1-6	Exposure to Investigational Product During Long-Term Extension Therapy Period / Safety Analysis Set
Table 14.1-7	Exposure to Investigational Product During Open-Label Extension Therapy Period / Safety Analysis Set
Table 14.1-8	Exposure to Investigational Product During Study / Safety Analysis Set
Table 14.2-1.1	Summary of Baseline and Change from Baseline of Modified Mayo Endoscopy (MMES) / Full Analysis Set
Table 14.2-1.2	Change from Baseline in MMES at Week 12 / Full Analysis Set
Table 14.2-2.1	UCEIS During Induction Therapy Period / Full Analysis Set
Table 14.2-2.2	Total Mayo Clinic Score at During Induction Therapy Period / Full Analysis Set
Table 14.2-2.3	Partial Mayo Clinic Score at During Induction Therapy Period / Full Analysis Set
Table 14.2-2.4	Clinical Improvement at Week 12 / Full Analysis Set
Table 14.2-2.5.1	Change from Baseline in UCEIS at Week 12 / Full Analysis Set
Table 14.2-2.5.2	Change from Baseline in Total Mayo Clinic Score at Week 12 / Full Analysis Set
Table 14.2-2.5.3	Change from Baseline in Partial Mayo Clinic Score at Week 12 / Full Analysis Set

Forms

Title Statistical Analysis Plan Template

Code	Version	Effective Date	Page
FRM_ST03_032	01	23 Apr 2015	41 of 53

Number	Title
Table 14.2-3.1.1	Summary of Score and Change from Baseline in MMES During Long-Term Extension Therapy Period / Full Analysis Set
Table 14.2-3.1.2	Summary of Score and Change from Baseline in MMES During Open-Label Extension Therapy Period / Full Analysis Set
Table 14.2-3.2.1	Summary of Score and Change from Baseline in UCEIS During Long-Term Extension Therapy Period / Full Analysis Set
Table 14.2-3.2.2	Summary of Score and Change from Baseline in UCEIS During Open-Label Extension Therapy Period / Full Analysis Set
Table 14.2-3.3.1	Summary of Score and Change from Baseline in Total Mayo Score During Long-Term Extension Period / Full Analysis Set
Table 14.2-3.3.2	Summary of Score and Change from Baseline in Total Mayo Score During Open-Label Extension Period / Full Analysis Set
Table 14.2-3.3.3	Summary of Score and Change from Baseline in Partial Mayo Clinic Scores During Long-Term Extension Therapy Period and Double-Blind Therapy Follow-Up Period / Full Analysis Set
Table 14.2-3.3.4	Summary of Score and Change from Baseline in Partial Mayo Clinic Scores During Open-Label Extension Therapy Period and Open-Label Extension Therapy Follow-Up Period / Full Analysis Set
Table 14.2-3.4.1	Summary Score and Change from Baseline in IBDQ Total Score During Long-Term Extension Therapy Period and Double-Blind Therapy Follow-Up Period / Full Analysis Set
Table 14.2-3.4.2	Summary Score and Change from Baseline in IBDQ Total Score During Open-Label Extension Therapy Period and Open-Label Extension Therapy Follow-Up Period / Full Analysis Set
Table 14.2-3.4.3	Summary Score and Change from Baseline in IBDQ - Bowel-Related Symptoms Score During Long-Term Extension Therapy Period and Double-Blind Therapy Follow-Up Period / Full Analysis Set
Table 14.2-3.4.4	Summary Score and Change from Baseline in IBDQ - Bowel-Related Symptoms Score During Open-Label Extension Therapy Period and Open-Label Extension Therapy Follow-Up Period / Full Analysis Set
Table 14.2-3.4.5	Summary Score and Change from Baseline in IBDQ - Systemic Function Score During Long-Term Extension Therapy Period and Double-Blind Therapy Follow-Up Period / Full Analysis Set
Table 14.2-3.4.6	Summary Score and Change from Baseline in IBDQ - Systemic Function Score During Open-Label Extension Therapy Period and Open-Label Extension Therapy Follow-Up Period / Full Analysis Set
Table 14.2-3.4.7	Summary Score and Change from Baseline in IBDQ - Social Function Score During Long-Term Extension Therapy Period and Double-Blind Therapy Follow-Up Period / Full Analysis Set
Table 14.2-3.4.8	Summary Score and Change from Baseline in IBDQ - Social Function Score During Open-Label Extension Therapy Period and Open-Label Extension Therapy Follow-Up Period / Full Analysis Set

Forms

Title Statistical Analysis Plan Template

Code

Version

Effective Date

Page

FRM_ST03_032

01

23 Apr 2015

42 of 53

Number	Title
Table 14.2-3.4.9	Summary Score and Change from Baseline in IBDQ - Emotional Status Score During Long-Term Extension Therapy Period and Double-Blind Therapy Follow-Up Period / Full Analysis Set
Table 14.2-3.4.10	Summary Score and Change from Baseline in IBDQ - Emotional Status Score During Open-Label Extension Therapy Period and Open-Label Extension Therapy Follow-Up Period / Full Analysis Set
Table 14.2-3.5.1	Summary Score and Change from Baseline in Corticosteroid (Glucocorticoid) Dosages During Long-Term Extension Therapy Period and Double-Blind Therapy Follow-Up Period / Full Analysis Set
Table 14.2-3.5.2	Summary Score and Change from Baseline in Corticosteroid (Glucocorticoid) Dosages During Open-Label Extension Therapy Period and Open-Label Extension Therapy Follow-Up Period / Full Analysis Set
Table 14.2-3.5.3	Summary Score and Change from Baseline in Duration of Corticosteroid-Free Treatment During Long-Term Extension Therapy Period and Double-Blind Therapy Follow-Up Period / Full Analysis Set
Table 14.2-3.5.4	Summary Score and Change from Baseline in Duration of Corticosteroid-Free Treatment During Open-Label Extension Therapy Period and Open-Label Extension Therapy Follow-Up Period / Full Analysis Set
Table 14.2-3.6	Percentage of Clinical Response at Week 52 During Double-Blind Therapy Period / Full Analysis Set
Table 14.2-3.7	Percentage of Clinical Response at Week 52 During Open-Label Extension Therapy Period / Full Analysis Set
Table 14.2-3.8.1	Change from Baseline in UCEIS at Week 52 During Double-Blind Therapy Period / Full Analysis Set
Table 14.2-3.8.2	Change from Baseline in Total Mayo Clinic Score at Week 52 During Double-Blind Therapy Period / Full Analysis Set
Table 14.2-3.8.3	Change from Baseline in Total Partial Clinic Score at Week 52 During Double-Blind Therapy Period / Full Analysis Set
Table 14.2-3.8.4	Mean Change from Baseline in Partial Mayo Clinic Scores During Double-Blind Therapy Period and Double-Blind Therapy Follow-Up Period / Mixed Model for Repeated Measures / Full Analysis Set
Table 14.2-3.9.1	Summary of Score and Change from Baseline in Mayo Clinic Score - Stool Frequency During Double-Blind Therapy Period and Double-Blind Therapy Follow-Up Period / Full Analysis Set
Table 14.2-3.9.2	Summary of Score and Change from Baseline in Mayo Clinic Score - Stool Frequency During Open-Label Extension Therapy Period and Open-Label Extension Therapy Follow-Up Period / Full Analysis Set
Table 14.2-3.9.3	Summary of Score and Change from Baseline in Mayo Clinic Score - Rectal Bleeding During Double-Blind Therapy Period and Double-Blind Therapy Follow-Up Period / Full Analysis Set
Table 14.2-3.9.4	Summary of Score and Change from Baseline in Mayo Clinic Score - Rectal Bleeding During Open-Label Extension Therapy Period and Open-Label Extension Therapy Follow-Up Period / Full Analysis Set
Table 14.2-3.9.5	Summary of Score and Change from Baseline in Mayo Clinic Score - Physician's Global Assessment During Double-

Forms

Title Statistical Analysis Plan Template

Code	Version	Effective Date	Page
FRM_ST03_032	01	23 Apr 2015	43 of 53

Number	Title
	Blind Therapy Period and Double-Blind Therapy Follow-Up Period / Full Analysis Set
Table 14.2-3.9.6	Summary of Score and Change from Baseline in Mayo Clinic Score - Physician's Global Assessment During Open-Label Extension Therapy Period and Open-Label Extension Therapy Follow-Up Period / Full Analysis Set
Table 14.2-3.9.7	Summary of Score and Change from Baseline in Modified Baron Endoscopic Score During Double-Blind Therapy Period / Full Analysis Set
Table 14.2-3.9.8	Summary of Score and Change from Baseline in Modified Baron Endoscopic Score During Open-Label Extension Therapy Period / Full Analysis Set
Table 14.2-3.9.9	Summary of Score and Change from Baseline in UCEIS Subscore - Vascular Pattern During Double-Blind Therapy Period / Full Analysis Set
Table 14.2-3.9.10	Summary of Score and Change from Baseline in UCEIS Subscore - Vascular Pattern During Open-Label Extension Therapy Period / Full Analysis Set
Table 14.2-3.9.11	Summary of Score and Change from Baseline in UCEIS Subscore - Bleeding During Double-Blind Therapy Period / Full Analysis Set
Table 14.2-3.9.12	Summary of Score and Change from Baseline in UCEIS Subscore - Bleeding During Open-Label Extension Therapy Period / Full Analysis Set
Table 14.2-3.9.13	Summary of Score and Change from Baseline in UCEIS Subscore - Erosions and Ulcers During Double-Blind Therapy Period / Full Analysis Set
Table 14.2-3.9.14	Summary of Score and Change from Baseline in UCEIS Subscore - Erosions and Ulcers During Open-Label Extension Therapy Period / Full Analysis Set
Table 14.2-8.1	Summary of Score and Change from Baseline in MMES During Double-Blind Therapy / Full Analysis Set
Table 14.2-8.2	Summary of Score and Change from Baseline in MMES During Open-Label Extension Therapy / Full Analysis Set
Table 14.2-8.3	Summary of Score and Change from Baseline in UCEIS During Double-Blind Therapy / Full Analysis Set
Table 14.2-8.4	Summary of Score and Change from Baseline in UCEIS During Open-Label Extension Therapy Period / Full Analysis Set
Table 14.2-8.5	Summary of Score and Change from Baseline in Total Mayo Score During Double-Blind Therapy Period / Full Analysis Set
Table 14.2-8.6	Summary of Score and Change from Baseline in Total Mayo Score During Open-Label Extension Period / Full Analysis Set
Table 14.2-8.7	Summary of Score and Change from Baseline in Partial Mayo Score During Double-Blind Therapy Period and Double-

Forms

Title Statistical Analysis Plan Template

Code	Version	Effective Date	Page
FRM_ST03_032	01	23 Apr 2015	44 of 53

Number	Title
	Blind Therapy Follow-Up Period / Full Analysis Set
Table 14.2-8.8	Summary of Score and Change from Baseline in Partial Mayo Score During Open-Label Extension Therapy Period and Open-Label Extension Therapy Follow-Up Period / Full Analysis Set
Table 14.3.1-1.1	Overall Summary of Treatment-Emergent Adverse Events During Study / Safety Analysis Set
Table 14.3.1-1.2	Summary of Treatment-Emergent Adverse Events During Double-Blind Therapy Period and Double-Blind Therapy Follow-Up Period / Safety Analysis Set
Table 14.3.1-1.3	Summary of Treatment-Emergent Adverse Events During Double-Blind Induction Therapy Period / Safety Analysis Set
Table 14.3.1-1.4	Summary of Treatment-Emergent Adverse Events During Open-Label Extension Therapy Period and Open-Label Extension Therapy Follow-Up Period / Safety Analysis Set
Table 14.3.1-2.1	Treatment-Emergent Adverse Events By System Organ Class and Preferred Term During Double-Blind Therapy Period and Double-Blind Therapy Follow-Up Period / Safety Analysis Set
Table 14.3.1-2.2	Treatment-Emergent Adverse Events By System Organ Class and Preferred Term Double-Blind Induction Therapy Period / Safety Analysis Set
Table 14.3.1-2.3	Treatment-Emergent Adverse Events By System Organ Class and Preferred Term During Open-Label Extension Therapy Period and Open-Label Extension Therapy Follow-Up Period / Safety Analysis Set
Table 14.3.1-2.4	Treatment-Emergent Adverse Events By System Organ Class, Preferred Term and Relationship to Investigational Product During Double-Blind Therapy Period and Double-Blind Therapy Follow-Up Period / Safety Analysis Set
Table 14.3.1-2.5	Treatment-Emergent Adverse Events By System Organ Class, Preferred Term and Relationship to Investigational Product During Double-Blind Induction Therapy Period / Safety Analysis Set
Table 14.3.1-2.6	Treatment-Emergent Adverse Events By System Organ Class, Preferred Term and Relationship to Investigational Product During Open-Label Extension Therapy Period and Open-Label Extension Therapy Follow-Up Period / Safety Analysis Set
Table 14.3.1-3.1	Treatment-Emergent Adverse Events By Maximum Severity, System Organ Class and Preferred Term During Double-Blind Therapy Period and Double-Blind Therapy Follow-Up Period / Safety Analysis Set
Table 14.3.1-3.2	Treatment-Emergent Adverse Events By Maximum Severity, System Organ Class and Preferred Term During Double-Blind Induction Therapy Period / Safety Analysis Set
Table 14.3.1-3.3	Treatment-Emergent Adverse Events By Maximum Severity, System Organ Class and Preferred Term During Open-Label Extension Therapy Period and Open-Label Extension Therapy Follow-Up Period / Safety Analysis Set
Table 14.3.1-4.1	Serious Treatment-Emergent Adverse Events By System Organ Class and Preferred Term During Double-Blind Therapy

Forms

Title Statistical Analysis Plan Template

Code	Version	Effective Date	Page
FRM_ST03_032	01	23 Apr 2015	45 of 53

Number	Title
	Period and Double-Blind Therapy Follow-Up Period / Safety Analysis Set
Table 14.3.1-4.2	Serious Treatment-Emergent Adverse Events By System Organ Class and Preferred Term During Double-Blind Induction Therapy Period / Safety Analysis Set
Table 14.3.1-4.3	Serious Treatment-Emergent Adverse Events By System Organ Class and Preferred Term During Open-Label Extension Therapy Period and Open-Label Extension Therapy Follow-Up Period / Safety Analysis Set
Table 14.3.1-5.1	Treatment-Emergent Adverse Events Leading to Discontinuation from The Study By System Organ Class and Preferred Term During Double-Blind Therapy Period and Double-Blind Therapy Follow-Up Period / Safety Analysis Set
Table 14.3.1-5.2	Treatment-Emergent Adverse Events Leading to Discontinuation from The Study By System Organ Class and Preferred Term During Double-Blind Induction Therapy Period / Safety Analysis Set
Table 14.3.1-5.3	Treatment-Emergent Adverse Events Leading to Discontinuation from The Study By System Organ Class and Preferred Term During Open-Label Extension Therapy Period and Open-Label Extension Therapy Follow-Up Period / Safety Analysis Set
Table 14.3.4-1.1	Vital Signs and Body Weight and Change from Baseline During Double-Blind Therapy Period and Double-Blind Therapy Follow-Up Period / Safety Analysis Set
Table 14.3.4-1.2	Vital Signs and Body Weight and Change from Baseline During Open-Label Extension Therapy Period and Open-Label Extension Therapy Follow-Up Period / Safety Analysis Set
Table 14.3.4-2.1	Summary of Clinical Laboratory Values-Hematology During Double-Blind Therapy Period and Double-Blind Therapy Follow-Up Period / Safety Analysis Set
Table 14.3.4-2.2	Summary of Clinical Laboratory Values-Hematology During Open-Label Extension Therapy Period and Open-Label Extension Therapy Follow-Up Period / Safety Analysis Set
Table 14.3.4-2.3	Summary of Clinical Laboratory Values- Serum Chemistry During Double-Blind Therapy Period and Double-Blind Therapy Follow-Up Period / Safety Analysis Set
Table 14.3.4-2.4	Summary of Clinical Laboratory Values- Serum Chemistry During Open-Label Extension Therapy Period and Open-Label Extension Therapy Follow-Up Period / Safety Analysis Set
Table 14.3.4-2.5	Summary of Clinical Laboratory Values- Coagulation Profile During Double-Blind Therapy Period and Double-Blind Therapy Follow-Up Period / Safety Analysis Set
Table 14.3.4-2.6	Summary of Clinical Laboratory Values- Coagulation Profile During Open-Label Extension Therapy Period and Open-Label Extension Therapy Follow-Up Period / Safety Analysis Set

Forms

Title Statistical Analysis Plan Template

Code	Version	Effective Date	Page
FRM_ST03_032	01	23 Apr 2015	46 of 53

Number	Title
Table 14.3.4-2.7	Summary of Clinical Laboratory Values- Urinalyses During Double-Blind Therapy Period and Double-Blind Therapy Follow-Up Period / Safety Analysis Set
Table 14.3.4-2.8	Summary of Clinical Laboratory Values- Urinalyses During Open-Label Extension Therapy Period and Open-Label Extension Therapy Follow-Up Period / Safety Analysis Set
Table 14.3.4-2.9	Shift Table of Clinical Laboratory Values -Hematology During Double-Blind Therapy Period and Double-Blind Therapy Follow-Up Period / Safety Analysis Set
Table 14.3.4-2.10	Shift Table of Clinical Laboratory Values -Hematology During Open-Label Extension Therapy Period and Open-Label Extension Therapy Follow-Up Period / Safety Analysis Set
Table 14.3.4-2.11	Shift Table of Clinical Laboratory Values - Serum Chemistry During Double-Blind Therapy Period and Double-Blind Therapy Follow-Up Period / Safety Analysis Set
Table 14.3.4-2.12	Shift Table of Clinical Laboratory Values - Serum Chemistry During Open-Label Extension Therapy Period and Open-Label Extension Therapy Follow-Up Period / Safety Analysis Set
Table 14.3.4-2.13	Shift Table of Clinical Laboratory Values -Coagulation Profile During Double-Blind Therapy Period and Double-Blind Therapy Follow-Up Period / Safety Analysis Set
Table 14.3.4-2.14	Shift Table of Clinical Laboratory Values -Coagulation Profile During Open-Label Extension Therapy Period and Open-Label Extension Therapy Follow-Up Period / Safety Analysis Set
Table 14.3.4-2.15	Shift Table of Clinical Laboratory Values - Urinalyses During Double-Blind Therapy Period and Double-Blind Therapy Follow-Up Period / Safety Analysis Set
Table 14.3.4-2.16	Shift Table of Clinical Laboratory Values - Urinalyses During Open-Label Extension Therapy Period and Open-Label Extension Therapy Follow-Up Period / Safety Analysis Set
Table 14.3.4-3.1	12-Lead Electrocardiogram Parameters During Double-Blind Therapy Period and Double-Blind Therapy Follow-Up Period / Safety Analysis Set
Table 14.3.4-3.2	12-Lead Electrocardiogram Parameters During Open-Label Extension Therapy Period and Open-Label Extension Therapy Follow-Up Period / Safety Analysis Set
Table 14.3.4-3.3	12-Lead Electrocardiogram: Summary of Elevated QTCF Values During Double-Blind Therapy Period and Double-Blind Therapy Follow-Up Period / Safety Analysis Set
Table 14.3.4-3.4	12-Lead Electrocardiogram: Summary of Elevated QTCF Values During Open-Label Extension Therapy Period and Open-Label Extension Therapy Follow-Up Period / Safety Analysis Set

Forms

Title Statistical Analysis Plan Template

Code

Version

Effective Date

Page

FRM_ST03_032

01

23 Apr 2015

47 of 53

Number	Title
Table 14.3.4-3.5	12-Lead Electrocardiogram: QTCF Change from Baseline - Categorical Analysis During Double-Blind Therapy Period and Double-Blind Therapy Follow-Up Period / Safety Analysis Set
Table 14.3.4-3.6	12-Lead Electrocardiogram: QTCF Change from Baseline - Categorical Analysis During Open-Label Extension Therapy Period and Open-Label Extension Therapy Follow-Up Period / Safety Analysis Set
Table 14.3.4-3.7	12-Lead Electrocardiogram: QTCF Categorical Analysis During Double-Blind Therapy Period and Double-Blind Therapy Follow-Up Period / Safety Analysis Set
Table 14.3.4-3.8	12-Lead Electrocardiogram: QTCF Categorical Analysis During Open-Label Extension Therapy Period and Open-Label Extension Therapy Follow-Up Period / Safety Analysis Set
Table 14.3.4-3.9	12-Lead Electrocardiogram: Shift Table of QTCF Values During Double-Blind Therapy Period and Double-Blind Therapy Follow-Up Period / Safety Analysis Set
Table 14.3.4-3.10	12-Lead Electrocardiogram: Shift Table of QTCF Values Open-Label Extension Therapy Period and Open-Label Extension Therapy Follow-Up Period / Safety Analysis Set

